13.5 Study Monitoring

Study monitoring will be performed in accordance with ICH E6-GCP, the Sponsor/CRO SOPs, the protocol, and applicable local regulations.

13.6 Audit and Inspection

According to ICH E6-GCP, the sponsor or regulatory authorities may audit the investigational site. The Sponsor's Quality Assurance Unit, independent of the Clinical Research and Development Department, is responsible for auditing the study.

The investigator(s) must accept that regulatory authorities may conduct an inspection to verify compliance of the study with GCP.

13.7 Insurance

This study is covered under the sponsor's Liability Insurance Policy (under General Electric Insurance Company and/or a company designated by the study sponsor). A Certificate of Insurance and/or an information leaflet containing essential information about the insurance coverage can be provided upon request.

13.8 Publication Policy

The investigator and/or Institution shall have the right to publish the results of their work conducted under this protocol, subject to providing the sponsor with the opportunity to review the contents of any proposed abstract or publication concerning the work, including any results of the study, in advance of publication and if necessary to delay publication for a limited time not to exceed 60 days in order to protect the confidentiality or proprietary nature of any information contained therein. The sponsor will make every reasonable effort to consider and release each proposed publication within 30 days, or proposed abstract within 15 days, of submission.

15 APPENDICES

15.1 Information on Investigational and Registered Products

The reference document for this study is the current SPC. The reference document provides up-to-date information on the efficacy and safety of Clariscan, and is used for assessing expectedness of serious adverse drug reactions, in order to determine regulatory reportability. An unexpected adverse drug reaction is a reaction, for which the nature, seriousness, severity or outcome is not consistent with the applicable product information, e.g., the SPC for the study drug.

15.2 Radiological Definitions and Classification of Adverse Events

Reference: [\[ESUR Guidelines 2017\]](#)

ACUTE ADVERSE REACTIONS

Definition: An adverse reaction which occurs within 1 hour of contrast medium injection.

The same acute adverse reactions are seen after iodine- and gadolinium-based contrast agents and after ultrasound contrast agents. The incidence is highest after iodine-based contrast agents and lowest after ultrasound agents.

Classification

Acute reactions are either allergy-like, hypersensitivity reactions or chemotoxic responses. Allergy-like reactions may or may not be true IgE-mediated allergy.

	Allergy-like/ Hypersensitivity	Chemotoxic
Mild	Mild urticaria Mild itching Erythema	Nausea/mild vomiting Warmth/chills Anxiety Vasovagal reaction which resolves spontaneously
Moderate	Marked urticaria Mild bronchospasm Facial/laryngeal oedema Vomiting	Severe vomiting Vasovagal attack
Severe	Hypotensive shock Respiratory arrest Cardiac arrest	Arrhythmia Convulsion

Note:

- Not all symptoms experienced by patients in the hour after contrast medium injection are adverse reactions to the contrast agent.
- Patient anxiety may cause symptoms after contrast medium administration (Lalli effect).
- When a new contrast medium is first introduced, adverse effects tend to be over-reported (Weber effect).

A.1.4. RECORDING ACUTE ADVERSE REACTIONS

- Acute adverse reactions must be properly documented in the patient's records, so that appropriate precautions can be taken before any future examination.
- All reactions requiring medical treatment should be recorded.
- Mild symptoms after contrast medium not requiring treatment should not be recorded. They may be unrelated to the contrast medium and caused by anxiety or by the patient's disease. If such minor symptoms are recorded, the patient may in future be denied a clinically important enhanced examination.
- Full documentation of acute allergy-like reactions includes (a) measuring serum tryptase, preferably immediately after and 2 hours after the reaction, and (b) skin testing one month after the reaction to check for evidence of true allergy to the triggering contrast agent and for evidence of cross-reactivity to other agents.

LATE ADVERSE REACTIONS

Definition:	A late adverse reaction to intravascular iodine-based contrast medium is defined as a reaction which occurs 1 hour to 1 week after contrast medium injection.
Reactions:	
Skin reactions similar in type to other drug-induced eruptions. Maculopapular rashes, erythema, swelling and pruritus are most common. Most skin reactions are mild to moderate and self-limiting.
 
A variety of late symptoms (e.g., nausea, vomiting, headache, musculoskeletal pains, fever) have been described following contrast medium, but many are not related to the contrast medium.

Risk factors for skin reactions:	
Previous late contrast medium reaction.
 
Interleukin-2 treatment.
 
Use of non-ionic dimers.

Management:	Symptomatic and similar to the management of other drug-induced skin reactions, e.g., antihistamines, topical steroids and emollients.
Recommendations:	
Patients who have had a previous contrast medium reaction, or who are on interleukin-2 treatment should be advised that a late skin reaction is possible and that they should contact a doctor if they have a problem.
 
Patch and delayed reading intradermal tests may be useful to confirm a late skin reaction to contrast medium and to study cross-reactivity patterns with other agents.
 
To reduce the risk of repeat reaction, use another contrast agent than the agent precipitating the first reaction. Avoid agents which have shown cross-reactivity on skin testing.
 
Drug prophylaxis is generally not recommended.

Note: Late skin reactions of the type which occur after iodine-based contrast media have not been described after gadolinium-based and ultrasound contrast media. **However, the Clariscan SPC does mention delayed reactions after one hour to few days' time.**

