
for emerging themes and patterns.
 
8. Challenges for radiology department will be assessed qualitatively for emerging patterns and themes.
 
Effectiveness Assessments:
 
1. Stage 1- Assessment by local radiologist/technician/nurse: Three parameters will be assessed for effectiveness of GBCAs, including Clariscan, by local radiologist (a & b) and technician/nurse (c) as first stage of assessment:
 
 Image quality reported by the local radiologist. Diagnostic confidence reported by the local radiologist. Customer satisfaction survey reported by the local nurse/radiology technician recorded once per centre during the study for each GBCA used at the study centre, including generics. 
2. Stage 2 - Assessment by expert panel: The second stage of analysis will be performed at a later date on a subgroup of patients. The anonymised images will be blindly analysed by an expert MR radiologist panel to assess the quality of images. The first 50 images will be analysed in a 1:1 ratio for Clariscan and other GBCAs, i.e., the first consecutive 25 images for Clariscan and the first consecutive 25 images of the other GBCAs (excluding liver-specific GBCAs). In total, a maximum of 850 patients' images will be transferred from all study centres. If sufficient number of images (25) for Clariscan or other GBCA group are not acquired in 3 months, the recruitment will stop at 3 months and all images for either group will be transferred for blinded read.
 
Images will be assessed for: a) Quality of images reported by 3 MR expert radiologists blinded to the GBCAs use and inter-observer variability, and b) Correlation between local radiologist rating and blinded radiologist rating.
 
Safety assessment:
 
Safety assessment will be based on spontaneously reported AEs for all GBCAs, including Clariscan. AE collection for spontaneously reported AEs and serious AEs (SAEs) will begin at the time of contrast medium injected and continue up to 7 days after GBCA use for individual patient, unless consent is withdrawn. AEs reported in the first hour after administration will be reported as "immediate" and any AEs reported after 1 hour and up to 7 days will be recorded as "delayed". All AEs will be tabulated as number reported and percentage:
 
 AEs, SAEs, severity of AEs, Clariscan vs GBCAs AEs, SAEs, severity of AEs, Clariscan vs individual GBCA 		

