6 STUDY DESIGN

6.1 Overall Study Design and Plan

A cross-sectional, multicentre (17 European Union [EU] centres), observational study with prospective data collection in patients undergoing contrast-enhanced MR (CE-MR) examination as part of routine clinical practice. Patients will be invited to participate in the study only after the decision has been made by the physician to use contrast agents and Clariscan is already included in the formulary of the hospital/institution as an independent decision prior to investigator taking part in this study. Patients enrolled in the study will not be actively followed up to collect adverse events (AEs) or outcomes. Any spontaneously reported AEs/information will be recorded/reported by the investigators up to 7 days after the MR procedure.

Enrolment

Patients: patients will only be approached to participate in the study after the physician has decided to use GBCA as part of routine clinical practice. Only patients who provide consent (directly or via a person with legal responsibility) will then be included in the study. To enable an understanding of the benefit of GBCAs use in a real world clinical setting the study plan to capture information in a maximum of 5,400 consecutive patients after the study centre has accepted to use Clariscan as an independent decision.

Recruitment will be based on **time (maximum 3 months – a month is equal to 30 calendar days) with a cap of a maximum number of cases per centre by country as defined in Table 1**. It will include all consecutive patients from the start of study after the Clariscan is on formulary of the study centre and available for routine clinical use. The decision to use GBCAs in the study centre/investigator will be made independent of the study after the centre has included Clariscan in the hospital/institution formulary.

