This study's safety monitoring plan is justifiable and adequate from a safety standpoint in view of the following:

- The design of the safety plan permits collection and comparison of the safety response to GBCAs in real life setting based on AEs reported voluntarily by the patient to the physician.
- Consideration of a 7-day documentation of AEs permits the evaluation of late-appearing adverse effects that may emerge or progress after the administration of GBCAs. In line with post-marketing requirements, the investigator will notify sponsor or regulatory authority of AEs he or she becomes aware of after the 7-day documentation interval.

- The measures used to assess effectiveness and safety are well-defined and reliable, and the proposed safety analyses are adequate to assess the effects of the administration of GBCAs.

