9.2 Post-Imaging Period

Safety measurements will be performed from GBCA administration until 7 days post-administration for AEs reported voluntarily by the patient. No follow-up safety assessment is required unless AEs are reported spontaneously by the patient or healthcare providers. However, AEs will be documented in line with the requirements applicable for use of medicines in general, irrespective of the documentation window.

The following information will be collected once at the end of the study:

- Customer satisfaction to be recorded by the local nurse/radiology technician once per centre for each GBCA used at the study centre, including generics
- Investigator information - cumulative numbers for the recruitment period (date of the first patient to date of last patient at the centre) of the study at the centre
- Centre information- cumulative numbers for the recruitment period (date of the first patient to date of last patient at the centre) of the study at the centre

The first 25 consecutive patients where Clariscan is used and the first 25 consecutive patients where any other GBCAs (all together 25 patients) is used, the images will be transferred for storage to allow a blinded image read by the expert MR radiology panel to be performed in a future analysis. If the recruitment is less than 25 for either group, then the total images done for the group (Clariscan or GBCAs) during the recruitment period will be transferred. If a patient has repeat imaging for technical reasons and the image is not readable and has been repeated for same indication/reason, then the second readable image will be transferred for storage and future analysis.

See Section 10.3 and the Study Schedule of Events Table ([Table 2](#)) for further details.

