10.3 Safety Assessments

Clariscan and any other GBCA used in this observational study are approved. Safety data will be collected, assessed and reported in accordance with post-marketing requirements. Clinical trial safety requirements do not apply.

[figure not shown]
The investigator(s) and the sponsor will review the safety data. The following safety data will be collected and evaluated:

AE collection for spontaneously reported AEs and serious AEs (SAEs) will begin at the time of contrast medium injected and continue up to 7 days after GBCA use for individual patient, unless consent is withdrawn. AEs reported in the first hour post-administration will be recorded as “immediate” and any AEs reported after 1 hour and up to 7 days will be recorded as “delayed”. Definition and examples of mild moderate and severe are mentioned in Section 15.2.

All AEs will be tabulated as number reported and percentage:

- 1 AEs, SAEs, severity of AEs, Clariscan vs GBCAs
- 2 AEs, SAEs, severity of AEs, Clariscan vs individual GBCA

Figure 4 Safety Profile

The radiological definition of ‘immediate’ and ‘delayed’ AEs and severity of AEs are in Section 15.2.

AE Definition: An AE is defined as any untoward medical occurrence in a patient or clinical investigation subject administered a pharmaceutical product and which does not necessarily have to have a causal relationship with this treatment. An AE can therefore be any unfavourable and unintended sign (including an abnormal laboratory finding), symptom, or disease temporally associated with the use of a study drug, whether or not considered related to that product. Only symptoms/signs that begin or worsen in severity and/or frequency after GBCA administration/use will be recorded as AEs in the eCRF.

The subjects will be closely observed and questioned with non-leading questioning (e.g., “How do you feel?”). The subjects will be instructed to immediately report any symptoms and signs to the study staff (i.e., between formal observations).

Both the investigator(s) and sponsor/CRO will perform a causality assessment on any AE, to assess whether or not there is a reasonable possibility (evidence to suggest) that the GBCAs caused the event.

Adverse Reaction: An AE that is caused by the GBCA.

Suspected Adverse Reaction: A reasonable possibility exists for causality between the GBCA and the AE.

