10.3.2 Adverse Event and Serious Adverse Event Reporting

Study centres are instructed to report all AEs to GEHC Global Pharmacovigilance within 3 days by sending an email to [contact].

The centre may ask questions or notify Global Pharmacovigilance Drug Safety Surveillance (DSS) Oslo that an AE report has been sent by calling [contact] ([contact]) during office hours.

Individual case safety reports of valid serious and non-serious adverse drug reactions will be classified as solicited reports from post-marketing source. The Sponsor will report adverse drug reactions (i.e., AEs for which a causal relationship is at least a reasonable possibility) to health authorities in accordance with Regulation (EC) No. 726/2004 and Sponsor standard operating procedures (SOPs).

Causally unrelated reports of AEs will be summarised as part of any interim safety analysis and in the final study report, where applicable.

Adverse reactions to other medicines than Clariscan will be handled according to Global Pharmacovigilance SOP SPV.19.01 (Section 5.5).

Events which affect the known risk-benefit balance of Clariscan and/or impact on public health will be notified to competent authorities and the Agency, in accordance with Global Pharmacovigilance SOP SPV.19.19.

The centre should also notify the Medical Director of the SAE at one of the contact numbers below.

For any protocol or safety-related questions please contact the Medical Director:

[name] [name]
Senior Medical Advisor
Life Sciences
GE Healthcare
[name]
[name]
Spain
T :[name]
M [name]
[contact]

All AEs should be recorded using acceptable diagnoses, if possible. If an AE has already been reported it is not necessary to report each individual sign and symptom of that AE as a separate AE. For example, if myocardial infarction is reported as an AE, there is no need to report elevated creatine kinase and abnormal electrocardiogram, or other related signs, symptoms, or laboratory values as separate AEs. However, if both occurred in isolation and myocardial infarction was not diagnosed, then each event would be reported as an AE.

The intensity of all AEs will be graded as mild, moderate, or severe using the following definitions:

Mild:	Tolerable.
Moderate:	Interferes with normal activity.
Severe:	Incapacitating (causes inability to perform usual activity or work).

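### Section 10.3 rests AE capture on both spontaneous reports and questioning, and Appendix 15.2 carries an unqualified instruction not to record mild untreated symptoms

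*Protocol*

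**What the plan says.** **Spontaneous capture.** The Synopsis states: "Safety assessment will be based on spontaneously reported AEs for all GBCAs, including Clariscan". Section 6.2 describes the safety comparison as "based on AEs reported voluntarily by the patient to the physician". Section 10.3 fixes the start: "AE collection for spontaneously reported AEs and serious AEs (SAEs) will begin at the time of contrast medium injected", continuing to day 7. Section 6.1 adds "Patients enrolled in the study will not be actively followed up to collect adverse events (AEs) or outcomes", and section 9.2 adds "No follow-up safety assessment is required unless AEs are reported spontaneously by the patient or healthcare providers".

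**Elicited capture.** Later in section 10.3, after the AE definition: "The subjects will be closely observed and questioned with non-leading questioning", with an open question about how the subject feels as the example. Section 10.3.2 classes valid adverse drug reaction reports as solicited.

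**Which AEs are kept.** Section 10.3 enters in the eCRF symptoms and signs that begin or worsen after the GBCA, with no severity threshold and whether or not related. Section 10.3.2 says "Study centres are instructed to report all AEs to GEHC Global Pharmacovigilance within 3 days" and grades all AEs as mild, moderate or severe. Appendix 15.2 says "Mild symptoms after contrast medium not requiring treatment should not be recorded".

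**What the data feed.** Sections 10.3 and 12.7 tabulate AE numbers and percentages for Clariscan, for the other GBCAs pooled and for each individual GBCA.

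**The concern.** AE percentages can be compared between agents only if events are looked for and kept in the same way for every agent. Section 6.2 claims that the safety plan permits such a comparison. An investigator reading section 10.3 could either wait for the patient to speak or ask each patient. An investigator who also reads 15.2 could leave out mild untreated symptoms.

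The agent is chosen at the site (sections 8.1.2 and 8.2), so capture practice and agent may both vary by centre. If they do, a difference in capture appears as a difference between agents. Appendix 15.2 itself warns that newly introduced contrast media attract excess reports, which is a further reason to fix one rule for a newly launched product. Events that were never elicited or recorded cannot be recovered at analysis.

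**Working it through.** The protocol states no expected AE rate, power or precision for safety, so there is no figure to reproduce. The check is a comparison of the text, followed by an illustration on assumed inputs.

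**1. Spontaneous against questioned**

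- Could questioning apply on site and spontaneous reporting only afterwards? Sections 6.1 and 9.2 allow this: they limit follow-up and do not forbid asking patients during the visit.
- Section 10.3 does not allow it as written. Its spontaneous rule begins at injection, so it covers the same on-site period as the questioning.
- The Synopsis and 6.2 describe the whole safety assessment as spontaneous or voluntary, with no exception for the visit.
- The contradiction therefore lies within 10.3, and between its questioning sentence and the Synopsis and 6.2.

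**2. Record all against omit mild untreated**

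| Source | Mild untreated symptom after GBCA |
|---|---|
| 10.3, AE definition | entered in the eCRF |
| 10.3.2 | reported and graded mild |
| 15.2, recording list | not recorded |

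The mild category in 15.2 includes nausea, warmth, mild itching and erythema. No statement says which text prevails.

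**3. Illustration (all inputs assumed)**

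Let s be the spontaneous AE rate, m the multiplier from questioning, q the share of acute AEs that are mild and untreated, and a the share of AEs that are acute (within 1 hour). Take s = 1%, m = 1.5 to 3, q = 50% to 80%. Counts use the planned maximum of 5,400 in section 12.9. The Table 1 caps sum to 200 + 900 + 1,200 + 1,000 + 300 + 250 + 900 = 4,750, but percentages and ratios do not depend on this.

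- Spontaneous: s = 1.0%, or 54 patients.
- Questioned: s × m = 1.5% to 3.0%, or 81 to 162 patients.
- Mild untreated acute AEs omitted: s × (1 − a × q). With a = 1 this is 0.5% down to 0.2% (27 down to 11 patients). With a = 0.5 it is 0.75% down to 0.6%.

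Now suppose equal true risk, with 70% of Clariscan patients and 30% of other patients at the centres that capture more.

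- Questioning against spontaneous, m = 1.5: Clariscan 0.7 × 1.5 + 0.3 × 1.0 = 1.35%; other 0.3 × 1.5 + 0.7 × 1.0 = 1.15%; ratio 1.17.
- The same, m = 3: 2.4% against 1.6%; ratio 1.5.
- Record-all against 15.2, a = 1: q = 50% gives 0.85/0.65 = 1.31; q = 80% gives 0.76/0.44 = 1.73.
- Record-all against 15.2, a = 0.5: q = 50% gives 0.925/0.825 = 1.12; q = 80% gives 0.88/0.72 = 1.22.

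The direction reverses if the 70/30 split reverses. With the same mix of agents at every centre, the ratio is 1.

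**The case against.** The strongest objection concerns 15.2. The text is reproduced under a guideline reference and keeps that guideline's own heading number. It deals with acute reactions, its list opens with the patient's records, and its reason is that a chart entry might deny the patient a later examination. The eCRF is not named. Section 10.3 points to 15.2 only for the severity and timing definitions. The same list describes tryptase and skin testing that do not appear in Table 2, so it cannot all be study instruction. A chart rule and an eCRF rule can coexist.

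Most of this stands, and it makes 15.2 the weaker of the two problems. It does not remove the need to clarify. Section 10.3 sends investigators to 15.2 twice. The sponsor adapted the appendix where the guideline did not fit, adding a closing remark on delayed reactions from the Clariscan SPC, but left the recording instruction unqualified.

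A reader might infer that there are three mutually exclusive rules, so that a centre can obey one only by breaking another. The documents do not support that: 6.1 and 9.2 limit follow-up without forbidding on-site questions, reporting all known AEs is compatible with spontaneous ascertainment, and 15.2 can be read as chart guidance.

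It is also fair to say that safety is part of a secondary objective and is tabulated descriptively. The 0.05 level in 12.6 applies to image quality and diagnostic confidence only.

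**Conclusion.** The point holds in two parts. Section 10.3 contradicts itself on whether AEs are spontaneous or elicited; this is firm and does not depend on the appendix. The unqualified recording text in 15.2 conflicts with 10.3 and 10.3.2; it is probably meant for the chart and acute reactions, but the protocol does not say so.

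The consequence is conditional. AE percentages may differ by centre practice. The Clariscan comparison is distorted only if the mix of agents also differs by centre. Every centre must have Clariscan on its formulary (7.2.1), and the protocol gives no usage data. It does provide for centres that fall short of 25 images for either group (7.1), so an uneven mix is foreseen but not established.

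A reader might take the illustrated ratios, about 1.1 to 1.7, as an expected bias, or conclude that 15.2 would remove most mild events from the safety record. Neither follows. The AE rate, mild share, acute share, questioning yield and centre split are all assumed, and the 15.2 text covers only acute reactions, so any delayed events reduce its effect. The inconsistency should be corrected whatever its size, because the text as written leaves the meaning of the safety percentages undefined.

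**What to change.** 1. State in 15.2 that its recording paragraph is guidance for the medical chart and does not govern study data. Every AE that begins or worsens after GBCA administration, including mild untreated ones, is entered in the eCRF.
2. Reconcile the Synopsis, 6.2 and 10.3 into one ascertainment rule applied alike to all centres and all GBCAs. Either of two would serve: spontaneous reports throughout, with the questioning sentence removed; or non-leading questioning on site, followed by spontaneous reports to day 7. The sponsor should choose one; what matters is that it is single and stated.
3. Label percentages that rest on spontaneous reports as reporting proportions, not incidence.

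If the second rule is chosen, an eCRF field marking each AE as elicited or spontaneous would allow separate tabulation; it is optional.

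The cost is wording in the protocol and eCRF guidance, and possibly slightly higher counts of mild AEs.
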